1. BACKGROUND AND RATIONALE

Peanut allergy is a common condition and is increasing in prevalence, with 1-2% prevalence in the pediatric population.(1) There has been a doubling of the number of peanut allergic children during a recent 10 year period.(2) The natural history of peanut allergy is persistence with resolution in only about 20% of children.(3) It is the most common cause of anaphylaxis in children presenting to the emergency room department.(4)

Currently, the only treatment for peanut allergy is strict avoidance and, if unintentional ingestion occurs, treatment with medications to prevent food anaphylaxis is warranted.(3) Unfortunately, when accidental ingestion occurs, anaphylaxis and death can occur.(5,6) Allergen avoidance affects the quality of life of the child and family, causes food related anxiety, and social limitation. Although other allergic conditions like allergic rhinitis and asthma can be treated with subcutaneous allergen immunotherapy, this traditional therapy is not feasible in peanut allergy because of the significant risk of systemic side effects, like death from anaphylaxis.(7,8)

Since subcutaneous immunotherapy to food is not feasible, oral immunotherapy trials have been performed with demonstrated safety and efficacy of this approach. Peanut allergy results from the breakdown of the immune system to maintain tolerance to peanut allergen. The gradual exposure to food proteins orally is thought to avoid acute allergic reactions by the induction of oral tolerance mechanisms like the production of inhibitory cytokines and regulatory T cells.(9-16) Desensitization, or a decreased clinical responsiveness to a defined amount of food allergen while consuming daily doses of the food, occurs through oral immunotherapy. Oral immunotherapy does not produce clinical *tolerance* of the food, defined as the ability to unrestricted amounts of the food antigen following a period of removal from daily dosing, but subjects are *desensitized*, defined as the ability to tolerate an increased amount of food without clinical symptoms after immunotherapy.

The process of desensitization through immunotherapy occurs after an initial food challenge to determine what amount of food allergen causes a clinical reaction in the subject. There are two phases in treatment with oral immunotherapy. In the first phase, the build-up phase, the subject ingests gradually escalating doses of peanut flour, administered orally in a vehicle once every day with weekly or bi-weekly dose escalation. Once a maintenance dose has been achieved, the subject continues to take this amount in a peanut equivalent dose over a period of years. Peanut equivalent dosing has been used in several prior peanut OIT trials without report of increased side effects or adverse events. (17-20) The peanut flour manufacturer for the initial trials in peanut oral immunotherapy by centers in the Consortium of Food Allergy Research (CoFAR) only provided dosing for the buildup phase for the trials and peanut equivalent dosing was used by centers for the maintenance phase. (Personal communication) Therefore, given the experience with peanut equivalent dosing, after the first year of this study, patients will be switched to a daily peanut equivalent dose and intake will be monitored by daily diaries. Since the daily dose will still be 3900 mg of peanut protein for the maintenance phase, the immunologic effects of the peanut dosing are not likely to be affected. (11, 12)

An open label study with an initial dose of 100 µg increased to 300 mg maintenance dose for several months demonstrated efficacy in over 90% of the subjects with desensitization and tolerance of a 3900 mg dose on food challenge.(11,12) A follow up double blind study

demonstrated efficacy with treated subjects tolerating 5000 mg compared to 280 mg in placebo subjects. The safety analysis of these studies demonstrated that 93% of children experienced symptoms on initial dosing day with 15% requiring epinephrine.(9) Most reactions were mild. However, when the initial dose was decreased from 50 mg down to 6 mg, allergic side effects were noted in only 47%. Of 10,184 home maintenance dosings of peanut flour, only 3.5% caused symptoms, with 2 subjects receiving epinephrine, each after one maintenance dose (0.02%). The relative safety of this approach has been demonstrated in these initial trials.(9)

Given the risk of clinical reactions to peanut allergen with accidental unintentional exposures and the impact of peanut avoidance on the quality of life of peanut allergic subjects (21), peanut immunotherapy as an effective treatment is an unmet need. This effective therapeutic procedure with an acceptable safety profile is needed in more academic centers around the country. Subjects receiving this therapy need close monitoring through expert centers to treat potential systemic symptoms. The immune determinants of clinical tolerance are still not completely understood. The goal of this proposed trial is to utilize the efficacy of oral immunotherapy to study the safety of peanut oral immunotherapy and evaluate immune mechanisms of clinical tolerance, using technology to identify T cell cytokine responses and subsets by flow cytometry. This trial will also expand the availability of this therapy to subjects in the southern United States.

All subjects will receive the peanut protein intervention. There is no placebo control for this study. In order to meet inclusion criteria subjects will not be able to tolerate a 1 gram peanut protein challenge. The primary outcome to be studied is the safety of the therapy and the secondary outcome will include changes in T and NKT cell function and intracellular cytokine expression from peanut allergic subjects during peanut OIT. We will look at both the initial response to building up the dose and changes during the maintenance phase. We are requesting a target enrollment of 15 subjects. Subjects will be recruited from the Texas Children's Hospital Allergy and Immunology Clinic. Subjects are expected to participate for a total of 38 months. After screening visits, the study will require approximately 33 visits with 2 phases: the build-up phase (weeks 0-50), followed by the maintenance phase (2 years).

2. OBJECTIVES

2.1 *Primary Objectives:*

- 2.1.1. The primary objective is to determine whether peanut oral immunotherapy safely develops clinical tolerance in peanut allergic patients by assessing the change of dose tolerated and to determine the percentage of subjects who can tolerate 6 g of peanut flour with absence of clinical symptoms during a food challenge following the initial desensitization phase of peanut flour which includes a 50 week dose escalation phase and 104 week maintenance phase on a peanut equivalent dose.

2.1. Secondary Objectives:

To determine the immune mechanisms of clinical tolerance, using technology to identify T cell cytokine responses and subsets, as well as basophil activation responses as measured by flow cytometry. T and NKT cell function and intracellular cytokine expression will be measured.

2.2.1. To determine whether viral exposure potentiates response to in vitro peanut allergen exposure and to assess those changes during peanut OIT.

2.2.2. To compare the change in dose tolerated after one month of abstaining from peanut to determine sustained unresponsiveness.

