The DBPCFC visit will last approximately 9 hours. The food challenge may be performed in one day or split into two days. The subject will discontinue antihistamines (for example Zyrtec or Claritin) for 7 days before the procedure and must be off oral corticosteroids for one month before the food challenge.

Peanut equivalent will be used for the food challenge. The challenge will consist of increasing doses of peanut (in the form of peanut flour and mixed with juice or baby food) given every 15 minutes in increasing amounts (Table 6). The other challenge will consist of placebo material given also in increasing doses. The highest dose of peanut flour will be equivalent to approximately 34 peanuts.

They will return 4 weeks after the 24 month food challenge for the 25 month food challenge. It will be conducted in the same manner as the 24 month food challenge. During this 4 week interval the subject must avoid peanut in his or her diet and will not take any peanut protein as he or she had been doing previously.

- Review Home Symptom Diary: At the 24 month visit we will review any symptoms experienced while taking the food protein.
- Urine Pregnancy Test: For females of reproductive potential a urine pregnancy test will be performed prior to the food challenge at both the 24 month and 25 month visits. If the subject is pregnant the food challenge will not be performed and the subject will be dismissed from the study.

Table 6.

24 and 25 Month Maintenance Phase Double-Blinded Placebo Controlled Food Challenge Protocol
--

Dose Number	Approximate Dose Weight (PEANUT PROTEIN)	Cumulative Dose Weight (peanut protein)
1	75 mg	75 mg
2	150 mg	225 mg
3	500 mg	725 mg
4	1000 mg	1725 mg
5	2000 mg	3725 mg
6	3000 mg	6725 mg
7	4000 mg	10725 mg
8	4500 mg	15225 mg
9	5000 mg	20225 mg
10	6000 mg	26225 mg

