Hypothesis: Polyfunctional flow cytometric analysis will elucidate differential T cell and invariant NKT cell activation responses involved in the expression of peanut allergy in subjects prior to and after desensitization through detection of the following.

- a. Cytokines: IL-2, IL-4, IL-10, IFN γ , IL-13, IL-12, IL-5, IL-17, CD152
- b. Transcription factors: GATA-3, T-bet, STAT-6, STAT-4
- c. Memory Cell Surface Markers: CCR-7, CD45RO
- d. Activation Surface Markers: CD40L, CD25, CD69, CD30, IL12RB2
- e. T regulatory markers: CD127, CD39, CD73, GARP, Foxp3

A TH2 CD4⁺ T cell response and invariant NKT cell response, characterized by the intracellular expression of GATA3, IL-4 and IL-13 will characterize the responses in peanut allergic subjects prior to desensitization and, afterwards, peanut allergic patients will have a CD4⁺ T cell response with a higher t-bet, IL-5, IL-10, INF γ , IL-17 and FOXP3 expression and an increased regulatory and memory T cell phenotype.

The clarification of the roles of TH1, TH2, TH17, iNKT and T regulatory peanut specific antigen responses in peanut allergic disease before and after desensitization will help define immune mechanisms involved in the expression of allergic inflammation in vivo in peanut allergy. T cell epitopes will be determined through tetramer technology on saved samples, requiring HLA typing of all participants through buccal mucosal scraping analysis. Gene profiling will be performed on samples as well. Furthermore, basophil histamine release assays will also serve as an additional measure to discriminate between individuals who have developed tolerance and those that have not. This research plan is likely to provide a framework for further investigation of responses underlying the development of IgE compared to non-IgE mediated food allergic disease.

SIGNIFICANCE:

Th1/Th2/Treg response

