9. MEASUREMENT OF EFFECT

9.1. Response Review:

The Data Safety Monitoring Committee will review the responses to the primary and secondary objectives every 6 months during the trial.

9.2. Response Criteria:

9.2.1. The primary objective will be measured by recording the daily symptoms experienced by the subjects and the number of subjects with no clinical symptoms during 6 g peanut flour challenge at time 50 weeks compared to time 0 weeks. The change in tolerated dose will be assessed between baseline and one year. The proportion of patients who tolerate 6 g of peanut flour will be compared at baseline and at the one year point using McNemar's test for matched pair data. The proportion of subjects will be estimated with exact binomial confidence intervals.

9.2.2. For the first secondary objective, flow cytometric analysis of T, NKT cells, and basophils will be performed through the measurement of the percent of cells producing a

cytokine as well as measuring surface and intracellular markers expressed upon activation and the significance of changes from time 0 to 1 year will be assessed as described below by using a paired t-test of the log-transformed data. Baseline measures of cell activation will be summarized by means with standard deviation. Normality will be assessed by quantile-quantile plots, and non-normality will be addressed by data transformations. A general linear mixed model will be used to estimate the effect of the therapeutic procedure over time. The model will include a fixed effect for time (discrete), and the matrix of correlated error terms will assume a first-order autoregressive structure. Alternative correlation structures such as the unstructured and compound symmetry will be considered. Correlation structures will be assessed by Akaike's Information Criteria. The likelihood ratio test will be used to test for overall significance of the model. P-values will be adjusted using the Holm's step down Bonferonni correction for multiple comparisons. Activation responses that are significant at the 0.05 level after adjustment will be further assessed. Pairwise comparisons between discrete time points will be tested for significant differences, and p-values will be adjusted using the Bonferonni correction. Statistical significance of the adjusted p-values will be assessed at the 0.05 level.

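### Objective 2.1.1 asks about clinical tolerance, but its challenge is taken during daily dosing, so under section 1's own definitions it supports a conclusion about desensitization only

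*Combined protocol and SAP*

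**What the plan says.** Section 1 separates two states. Clinical tolerance is "defined as the ability to unrestricted amounts of the food antigen following a period of removal from daily dosing" (a verb such as consume seems to have dropped out), and the same sentence says that OIT does not produce it. Desensitization is "a decreased clinical responsiveness to a defined amount of food allergen while consuming daily doses of the food".

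Objective 2.1.1 is to "determine whether peanut oral immunotherapy safely develops clinical tolerance in peanut allergic patients by assessing the change of dose tolerated", together with the percentage who tolerate 6 g of peanut flour without symptoms. It places the challenge after a treatment period "which includes a 50 week dose escalation phase and 104 week maintenance phase on a peanut equivalent dose".

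Section 9.2.1 gives a different time. It counts "the number of subjects with no clinical symptoms during 6 g peanut flour challenge at time 50 weeks compared to time 0 weeks", and the proportion "will be compared at baseline and at the one year point using McNemar's test for matched pair data".

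The first secondary objective seeks the immune mechanisms of clinical tolerance. Its paired test in section 9.2.2 runs from time 0 to 1 year.

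One scheduled challenge follows a break from peanut. Section 6.7 repeats the Month 24 challenge 4 weeks later and says: "During this 4 week interval the subject must avoid peanut in his or her diet". That comparison is secondary objective 2.2.2, labelled sustained unresponsiveness, and is analysed in section 9.2.4.

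**The concern.** The primary objective names an outcome that section 1 says the treatment does not produce, and it assesses that outcome under the conditions section 1 uses to define the other one. A good primary result would therefore be reported against a question that the design did not put to the children.

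What is at stake is the stated conclusion of the trial. A child who passes a challenge while eating peanut every day has shown desensitization. Whether the effect outlasts dosing is a separate question, asked only at Month 25. If 2.1.1 stands, a report that follows it can call on-treatment passes clinical tolerance and attach the same label to the immune changes measured at one year.

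**Working it through.** No figure in the plan decides this point. The sample size in section 10.1 concerns interferon-gamma and plays no part. The check sets the definitions against the schedule.

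**Step 1: criteria from section 1.** Tolerance has two parts: (a) a period of removal from daily dosing, and (b) unrestricted amounts. Desensitization is judged during daily dosing. The same paragraph also describes it as tolerating an increased amount without symptoms after immunotherapy, which is close to the change in tolerated dose named in 2.1.1.

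**Step 2: scheduled dosing status at each challenge after treatment starts.**

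| Challenge | Role | Daily peanut before it? | Source |
|---|---|---|---|
| Month 0 (about one year) | Primary time point in 9.2.1 | Yes. The daily equivalent dose starts at the Month 0 visit, and the challenge falls within 1 month of it | 6.5, 6.6; schedule of procedures marks OIT maintenance at Visit 30 |
| Month 24 (50 + 104 = 154 weeks) | Primary time point in 2.1.1 | Yes. The dose continues for 24 months, and avoidance begins only after this challenge | 6.5, 6.7 |
| Month 25 | Secondary, 2.2.2 and 9.2.4 | No. 4 weeks of avoidance | 6.7 |

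The maintenance row of the schedule stops at Visit 33, before Month 24, but the text of 6.5 and 6.7 leaves no planned gap before that challenge.

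**Step 3: compare.**
- Part (a), removal from dosing: met by 0 of the 2 possible primary challenges and by 1 of the 3 post-treatment challenges.
- Part (b), unrestricted amounts: met by none of the 3. Tables 5 and 6 both stop at a 6000 mg dose of peanut protein, 26,225 mg cumulative.
- Both parts: met by 0 of 3.

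The result does not depend on which primary time point is intended. The difference between 50 weeks and 154 weeks needs reconciling, but it is a separate matter.

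**Step 4: the immune objective.** At 1 year no off-peanut challenge has yet been scheduled, so the paired test in 9.2.2 describes change with desensitization. The hypothesis in section 6.10 (Scientific Rationale for Immune Cell Response Studies) already speaks of responses before and after desensitization.

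**Step 5: how much an immune comparison by Month 25 outcome could show.** Assume that the 50% attrition in section 10.1 applies to all 15 enrolled: 15 × 0.5 = 7.5, so 7 or 8 children. The exact 95% interval for 4 of 8 keeping their response is 15.7% to 84.3%. Section 6.10 lists 9 + 4 + 2 + 5 + 5 = 25 markers. Such a comparison could only be descriptive.

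**The case against.** The best reply is that this is terminology. Objective 2.1.1 says how its aim will be measured, section 1 names safety as the primary outcome, and each planned quantity can be estimated. That stands. A reader might infer that the primary endpoint is invalid, and it is not: only the step from the estimates to the word tolerance fails.

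Several other strong readings also go beyond the documents:

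- *The analysis counts on-treatment passes as tolerance.* Sections 9.2.1 and 9.2.2 do not use the phrase clinical tolerance, and no rule there classifies a child as tolerant. The fault lies in the objectives.
- *The design ignores the distinction.* It does not. Objective 2.2.2 and section 9.2.4 already keep sustained unresponsiveness for the off-peanut challenge.
- *The immune analysis cannot reach the off-peanut state.* Blood is drawn at Visits 34 and 35, and the mixed model and pairwise time contrasts in 9.2.2 can use it. They have no term for challenge outcome.
- *No child can be off peanut at one year.* Section 6.12 keeps willing discontinued participants in follow-up, with blood draws on a peanut-restricted diet. The statement holds for the schedule, not for every child.
- *Tolerance status cannot be known before Month 25.* Section 6.10 wants basophil assays as an "additional measure to discriminate between individuals who have developed tolerance and those that have not", and it glosses level of tolerance as the highest dose tolerated clinically. In that sense status can be read at any challenge. The gloss does not rescue 2.1.1, which uses the exact phrase that section 1 defines.

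**Conclusion.** The point holds as a mismatch between the stated objective and what the design can show. Neither candidate primary challenge follows a removal period, so a conclusion about clinical tolerance cannot follow from either. Conclusions about desensitization and safety can.

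A reader might take Month 25 as the test of tolerance. The documents do not support that either: it comes after only 4 weeks of avoidance and has a capped dose, whereas section 1 speaks of unrestricted amounts. Sustained unresponsiveness, the plan's own term, is the most it can show.

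A reader might also size the overstatement as the share of Month 24 passers who react at Month 25. The documents give no such share. The primary analysis in 9.2.1 uses one year, and no off-dosing challenge directly follows Month 0. Nor is there support for saying that families would be led to stop dosing: section 6.8 brings children back within 7 days of the food challenge for an exit maintenance dose.

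The verdict assumes that section 1's definition governs the phrase in 2.1.1 and that children dose as scheduled.

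**What to change.** 1. In 2.1.1, replace clinical tolerance with desensitization.
2. In the first secondary objective, describe the baseline-to-1-year immune change analysed in 9.2.2 as a change with desensitization.
3. State that any off-treatment conclusion rests only on the Month 25 challenge (2.2.2 and 9.2.4), is called sustained unresponsiveness after 4 weeks of avoidance, and is not called tolerance because that challenge is capped.
4. Leave the wording of 9.2.1 as it is on this point, since it does not use the phrase.
5. Optionally, as exploratory and descriptive only, report the immune and basophil results from Visits 34 and 35 by Month 25 outcome, with that outcome defined beforehand.

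Items 1 to 3 change wording only: no visit, sample, test or estimate is affected. Item 5 uses blood already scheduled and would be imprecise. The downside is a less ambitious stated claim.

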3. PATIENT ENROLLMENT CRITERIA

3.1. Inclusion Criteria:

Subjects who meet all of the following criteria are eligible for enrollment as study participants:

- Age 5-16 years of either sex, any race, any ethnicity, weighing at least 18.3 kg at the time of the initial visit.
- The presence of IgE specific to peanuts (a positive skin prick test to peanuts (diameter of wheal >3.0 mm) and a positive in vitro IgE [CAP-FEIA] > 7 kU/L).
- Significant clinical symptoms occurring within 120 minutes after ingestion of the last tolerated dose of peanut protein during the DBPCFC. Patients who have not had previous oral exposure to peanut will be observed for a longer duration of 150 minutes because they may demonstrate a delayed immune response, given the lack of prior peanut exposure. Also, patients with a history of prior anaphylaxis will be observed for 150 minutes. (21-24)
- Provide signed informed consent.
- Ability to follow-up regularly for scheduled appointments.
- Subjects will not be excluded if they are primarily Spanish speaking.
- Females of childbearing potential must be willing to practice an acceptable form of birth control throughout the protocol.
- Epinephrine injection training provided
- Participant has current in-date epinephrine injector and parent/guardian demonstrates proper use.

3.2. Exclusion Criteria

Subjects who meet any of the following criteria are not eligible for enrollment as study participants:

- History of severe anaphylaxis to peanut as defined by hypoxia, hypotension, or neurological compromise (Cyanosis or SpO₂ < 92% at any stage, hypotension, confusion, collapse, loss of consciousness; or incontinence)
- Currently participating in a study using an investigational new drug.
- Participation in any interventional study for the treatment of food allergy in the past 12 months or while participating in this study.
- Poor control or persistent activation of atopic dermatitis.
- Diagnosis of persistent asthma as defined by NHLBI criteria and currently being treated with daily doses of inhaled corticosteroids or requiring a rescue inhaler more than 2 days per week.
- Inability to discontinue antihistamines for skin testing and Oral Food Challenges (OFCs).
- Pregnant female.
- Chronic medical condition requiring frequent use of oral steroids, chronic psychiatric illness or history of substance abuse.
- Active eosinophilic esophagitis requiring medication therapy during the past 12 months
- Subjects with known oat or wheat allergy
- Subjects currently on the build-up phase of environmental allergy immunotherapy injections
- Live more than 175 miles away from Texas Children's Hospital located in the Medical Center.

NOTE:

Treatment of glucocorticoids (i.e. prednisone, methylprednisolone, and prednisolone) is permitted while on the study for subjects with wheezing and/or undiagnosed asthma. The dosing allowed will be no more than 2 mg/kg up to 21 days. Subjects will be taken off the study if treatment with any dose of steroid is required for greater than 21 days or if oral systemic corticosteroids are required greater than twice per year for asthma exacerbations.

